## 14 STUDY PROCEDURES

### 14.1 Subject Recruitment and Consent

Interested subjects, who respond to recruitment materials and are available to stay in the hospital or clinic for the 7-day Inpatient Treatment part of the study, will be scheduled to meet with a qualified investigative staff member and receive an explanation of the study purpose and requirements in lay language. During the initial interview, the interviewer should not ask questions in a manner that reveals the eligibility criteria for study entry.

If still interested after receiving an explanation of the study, subjects will be given an opportunity to review, inquire about, and sign the study informed consent form (see [Section 16.4](#)). The subject will then be given a copy of the signed consent form. After collecting demographic information (date of birth, gender, race, and ethnicity), site personnel will access the IWRS to obtain a unique subject number. Subjects will proceed to the screening phase of the study. Screening assessments must be completed within a 7-day time period, but can be completed as early as screening day 1, and randomization may be performed on the next calendar clinic visit day. Subjects must be randomized no later than the 7th day of screening (Day 1). At no time during the screening process should individuals

be given information regarding inclusion or exclusion criteria, with the exception that subjects will be informed that they must exhibit signs of opioid withdrawal immediately before randomization into the study. When individuals are evaluated, questions should be asked in a way that the criteria are not discernible.

Any subject who has difficulty understanding the information contained in the consent form will reread the misunderstood portion(s) of the consent and discuss with a research staff member until s/he shows complete understanding of the information in the consent form, and may thus give full consent. Subjects must complete a consent quiz with 100% accuracy before being randomized. Research staff will work closely with the subject in an effort to help them understand the requirements of their participation. Subjects with literacy problems will be assisted to the extent possible.

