### **14.3.2 Subject Randomization**

A prospective subject who meets all of the study inclusion criteria and does not meet any of the exclusion criteria may be randomized into the study. The final eligibility criterion is a score of at least 2 on the OOWS-Handelsman at Baseline.

A stratified randomization procedure will be used to separately allocate male and female subjects in 1 of the 3 treatment groups: 2.4 mg lofexidine, 3.2 mg lofexidine, or placebo. Randomization will be implemented centrally, that is, take place across all investigational sites using an Interactive Web Response System (IWRS) managed by the CRO

Once eligibility criteria are confirmed at the Baseline visit, site personnel will access the IWRS and complete randomization procedures. The system will assign a unique kit number for drug dispensation according to the randomization scheme. The subject number assigned at screening should be used throughout the study in all source documents and eCRFs.

The Site Investigator or study coordinator will arrange for hospital or clinic admission (in the event that the subject was not admitted the night before randomization) of the subject and for investigational agent to be dispensed to initiate treatment. Even if a subject does not actually receive any investigational agent after s/he has been randomized, s/he is considered to be in the intent-to-treat (ITT) population. should be notified of any irregularities that occur during randomization.

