#### **14.3.3 Days 1-7 (Randomized, Double-Blind, Placebo-Controlled Treatment)**

After randomization, subjects will receive their first dose of study medication (lofexidine or placebo) during the 8 AM dosing window on Day 1. Subjects will be dosed 4 times daily from Day 1 through Day 7 at 8 AM, 1 PM, 6 PM, and 11 PM. Vital signs will be recorded within 30 minutes before every dose and 3.5 hours after the 8 AM, 1 PM, and 6 PM dose. Other clinical assessments will be gathered between 11:00 AM and noon each day. These clinical assessments are described in detail in [Sections 15.4](#) and [15.5](#).

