**Table 1. Schedule of Study Assessments**

Activity	Randomized, Double-Blind, Placebo-Controlled (Days 1-7) followed by Open-Label, Continuation Treatment (Days 8-14)				Study Discontinuation/ End of Study*
	Screening Days -6 to -1	Baseline Day 1	Inpatient Treatment Days 1-7	In/Outpatient Treatment Days 8-14	
Informed Consent Signed	X				
Screening Number Assigned	X				
Inclusion/Exclusion Criteria	X	X (b)			
Prior Medication History	X	X (b)			
Demographics	X				
Medical and Smoking History	X				
Mini-International Neuropsychiatric Interview	X				
Infectious Disease Assessments (c)	X				
Pregnancy Test (d)	X	X			X
Height	X				
Weight	X				X
Admission to Inpatient Unit		X			
Randomization		X			
Study Medication Administration			X (QID)	X (variable)	
Medication Compliance			X	X	X
Discharge from Inpatient Unit			Day 7		
Efficacy Assessments					
Short Opiate Withdrawal Scale of Gossop (e)		X	X	X	X
Objective Opiate Withdrawal Scale of Handelsman (e)	X	X (f)	X	X	X
Modified Clinical Global Impression (e)			X	X	X
Visual Analog Scale for Efficacy (e)			X	X	X
Clinical Opiate Withdrawal Scale (e)	X	X	X	X	X
Concomitant Medications Assessment			X	X	X
Assessment of Detoxification Completion			X (g)	X	X
Safety Assessments					
Adverse Events Assessment			X	X	X
Vital Signs (Sitting/Recumbent & Standing BP and pulse; respiration, and temperature)	X	X	X (i)	X (j)	X
12-Lead Electrocardiogram (duplicate)	X (k)		X (l)	Day 8 and 14 (m)	X
Pharmacokinetic Sampling			X (n)		
Pharmacokinetic Sampling			Day 3 and 6 (r)		
Clinical Laboratory Tests (hematology, chemistry, urinalysis)	X		X (o)	X (o)	X
Physical Exam (p)	X	X	X	X	X

209229

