## 15.2 Baseline Assessments

The Baseline period is the morning of admission to the study, before randomization and dosing. Prospective subjects who meet all eligibility criteria must be randomized to the study in time to give the first dose of study medication at 8 AM.

The assessments listed below will be performed during the Baseline period.

- OOWS-Handelsman (score must be  $\geq 2$  for randomization).
- SOWS-Gossop.
- COWS.
- Vital signs (resting [sitting or recumbent, if applicable]) and standing blood pressure and pulse; respiration, temperature) measurements.
- Repeat pregnancy assessment (by “dipstick”), if female.
- Repeat urine drug screen (by “dipstick”).
- Update Inclusion/Exclusion Criteria form to reflect Baseline assessments.
- Update prior medication form and physical examination form to capture any new medications and/or medical problems since screening.
- Columbia Suicide Severity Rating Scale (C-SSRS) (Baseline version; Appendix 9).

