### **16.7 Adverse Event Reporting**

In accordance with FDA reporting requirements, all AEs occurring during the course of the clinical trial will be collected, documented, and reported by the Site Investigator or sub-investigators according to the specific instructions detailed in this section of the protocol and [Appendix 6](#). The occurrence of AEs will be assessed starting at the treatment phase of the protocol.

An AE is defined as any reaction, side effect, or untoward event that occurs during the course of the clinical trial, whether or not the event is considered related to the investigational agent or clinically significant. For this study, events reported by the subject, as well as clinically significant abnormal findings in the opinion of the Investigator on physical examination, laboratory evaluation, or C-SSRS (for example, score of 3 or more on the scale) will be considered an AE and will be recorded in the subject's source document and on the AE eCRF. A new illness, symptom, sign or clinically significant clinical laboratory abnormality or worsening of a pre-existing condition or abnormality is considered an AE. Stable chronic conditions, such as arthritis, which are present before clinical trial entry and do not worsen are not considered AEs.

After each AE assessment, the physician will record in the subject's source document and on the AE eCRF the type of AE and whether serious (SAE) or non-serious, severity of each AE, and the relationship to the study agent. These categories are asking for the physician's best judgment of the severity and relatedness of each AE. The physician will also record, based on his/her best judgment, whether the AE is secondary to opioid withdrawal (see [Section 15.4.8](#)). In general, an AE should not be marked as withdrawal related AND related to study medication.

Each day, a study physician must review any AEs that are reported as beginning or as continuing. All AEs, including clinically significant abnormal findings on laboratory evaluations, regardless of severity, will be followed by a study physician until satisfactory resolution.

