6.2 Derived Data

• Definition of baseline

For all variables, baseline is defined as the last non-missing value prior to the receiving the first dose of study medication.

All tabulations involving change from baseline data will only include subjects with cohort data i.e. with data at baseline and at follow-up. Change from baseline will be calculated as follow-up values minus baseline value.

• Incomplete dates

All incomplete dates will be included in the clinical database as they were entered in the eCRF. Thereafter for calculation purposes, the incomplete dates will be completed using pre-defined rules. If a day or month is not recorded it will be replaced by the first day of the month or January respectively, provided this does not contradict any other dates recorded. For missing adverse events and medications dates/times during the trial, the worst-case date will be used (e.g. the end of the month for a stop date and 23:59 for the stop time, the date/time of initial dose for start of AE i.e. all events with missing start dates will be assumed to be treatment emergent).

• Ambiguous values

In the case where a variable is recorded as ">x", " \geq x", "<x" or " \leq x", then for analysis purposes a value of x will be taken. Where a range of values is quoted the midpoint of the range will be taken.

Effective: 14-Feb-13

Page 6 of 26

• Questionnaire Data

In the event that component items used to calculate total scores for questionnaire data e.g. SOWS Gossop score are missing then the total scores will also be set to missing.

• Site pooling for statistical analyses

For the purposes of statistical analyses models where site is included within the model as a fixed effect, sites randomizing < 6 subjects will be pooled from smallest to largest until the pooled site subsequently created has at least 6 subjects. In the event that the pooling of sites with less than 6 subjects does not result in a site with > 6 subjects, then that pooled site with < 6 subjects will also be pooled with the next largest site with > 6 subjects. To break ties if more than one site has the same number of subjects, the site identifier will be used as a secondary sort key.

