All AEs will be listed and tabulated by severity, relationship to study medication, primary system organ class and preferred term according to MedDRA Version 16.0. In counting the number of events reported, a continuous event, i.e., an event reported more than once and which did not cease, will be counted only once with the worst recorded severity; non-continuous AEs reported several times by the same subject will be counted as multiple events. Events present immediately prior to the first dose of study medication that do not worsen in severity, will not be regarded as treatment emergent. Events with start dates more than 30 days after the administration of the last dose of study medication will not be considered treatment emergent and will be listed separately. In deriving the tabulation relating to preferred term reporting, the severity of a recurrent AE will be taken to be the most severe and the relationship to study medication as the highest probable.

The following will be summarized and presented for the overall population and by treatment group:

- The number and percentage of subjects experiencing at least 1 treatment emergent TEAE by MedDRA preferred term and SOC. A chi-squared test will be used to test for a difference in the percentage of subjects experiencing at least 1 TEAE between each of the 2 Lofexidine doses and placebo.
- The number and percentage of subjects experiencing an opioid withdrawal related TEAE by MedDRA preferred term and SOC.
- The number and percentage of subjects experiencing TEAEs by severity of event
- The number and percentage of subjects experiencing TEAEs by relationship to IP
- The number and percentage of subjects experiencing treatment-related adverse events (i.e. Possibly Related, Probably Related, Definitely Related)
- The number and percentage of subjects experiencing at least 1 treatment emergent SAE by MedDRA preferred term and SOC
- The number and percentage of subjects experiencing SAEs by severity of the event
- The number and percentage of subjects experiencing SAEs by relatedness to IP

Adverse events whilst receiving Lofexidine therapy during the open-label phase

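### The SAP's treatment-emergence rule needs each symptom's severity before the first dose, but the protocol schedules no pre-dose adverse-event query in subjects who are already in withdrawal

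*Protocol*

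**What the plan says.** **The rule.** For the double-blind phase, SAP 6.13 states: "Events present immediately prior to the first dose of study medication that do not worsen in severity, will not be regarded as treatment emergent". Neither SAP addendum changes this. The same section tests the percentage of subjects with at least one TEAE, each lofexidine dose against placebo, by chi-squared.

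**The collection schedule.** In protocol Table 1 the row "Adverse Events Assessment" has an X for Days 1-7, Days 8-14 and Study Discontinuation/End of Study, and nothing under Screening or Baseline. The Baseline list in 15.2 has no adverse-event question. Its nearest item is "Update prior medication form and physical examination form to capture any new medications and/or medical problems since screening". Section 16.7 says: "The occurrence of AEs will be assessed starting at the treatment phase of the protocol". For Days 1-7, section 14.3.3 adds: "Other clinical assessments will be gathered between 11:00 AM and noon each day". The first dose is in the 8 AM window.

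**The population.** Section 14.3.2: "The final eligibility criterion is a score of at least 2 on the OOWS-Handelsman at Baseline". Section 14.1 says that candidates are told "they must exhibit signs of opioid withdrawal immediately before randomization into the study".

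**The default.** Under SAP 6.2, "all events with missing start dates will be assumed to be treatment emergent".

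**The concern.** The SAP rule compares an event's severity just before the first dose with its severity afterwards. The adverse-event data as scheduled hold only the second half of that comparison. In many trials the gap would affect few subjects. Here entry requires active withdrawal, and the signs that qualify a subject (cramps, anxiety, tremor, sweating, vomiting) can also be reported as adverse events.

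A symptom present at 7 AM and first mentioned at the late-morning assessment may be dated to Day 1 and counted as treatment-emergent. It may instead be dated earlier, with its pre-dose severity resting on recall after dosing. If the start date is missing, the default makes it treatment-emergent.

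What is at stake is the safety comparison. The study objectives ask whether the lower dose gives fewer and less severe adverse events, and SAP 6.13 tests each dose against placebo. Background symptoms in the TEAE counts blur those contrasts for every term that overlaps with withdrawal.

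**Working it through.** **Step 1: what the rule needs and where it could come from.**

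| Source before the first dose | Presence of the symptom | Severity | Linked to the TEAE rule? |
|---|---|---|---|
| AE record (Table 1, 15.2) | not scheduled | not scheduled | would be the direct input |
| Physical-exam form update (15.2) | new medical problems | no grade mentioned | no |
| SOWS-Gossop at Baseline (15.2, Table 2) | 10 items | none to severe | no |
| COWS at Baseline (15.2, 15.4.5) | 11 items | item scores reflect severity | no |
| OOWS-Handelsman at Baseline (15.4.2) | 13 signs | present or absent | no |

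Graded symptom data therefore exist before dosing, but no text tells the analyst to use them to set treatment emergence. Section 15.4.8 keeps scale items and adverse events apart: an item does not automatically become a withdrawal-related event.

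**Step 2: the start of collection.** Section 16.7 begins at the treatment phase. Section 14.3 carries that title, and its first subsection is 14.3.1, Baseline. On that reading collection starts before randomization, which Table 1 and 15.2 do not carry through. On the other reading it starts with dosing, and the SAP rule lacks its input. The passages need reconciling either way.

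**Step 3: the effect on a difference.** The documents give no pre-dose symptom rate, no TEAE rate and no power for the TEAE test, so there is no stated figure to reproduce and what follows is illustration. Let r be the new-onset rate in an arm and p0 the share of subjects whose pre-existing symptom is counted, equal across arms:

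- observed rate = p0 + (1 − p0) × r
- observed difference = (1 − p0) × (r on lofexidine − r on placebo)

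Inputs: 225 and 150 subjects (protocol 10.2); two-sided 0.05 (SAP 6.1); r = 25% on lofexidine and 10% on placebo (assumed). Power uses the normal approximation to the chi-squared test, Φ((d − 1.96 × se0)/se1), with se0 from the pooled rate and se1 from the separate rates.

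For p0 = 0.30 the rates are 0.30 + 0.70 × 0.25 = 0.475 and 0.30 + 0.70 × 0.10 = 0.370, so d = 0.105. The pooled rate is (150 × 0.370 + 225 × 0.475)/375 = 0.433. Then se0 = √(0.433 × 0.567 × (1/150 + 1/225)) = 0.0522 and se1 = √(0.370 × 0.630/150 + 0.475 × 0.525/225) = 0.0516. Power = Φ((0.105 − 0.1024)/0.0516) = 0.52.

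| p0 | Lofexidine | Placebo | Difference (points) | Power |
|---|---|---|---|---|
| 0 | 25.0% | 10.0% | 15.0 | 0.97 |
| 5% | 28.75% | 14.5% | 14.25 | 0.91 |
| 10% | 32.5% | 19.0% | 13.5 | 0.83 |
| 30% | 47.5% | 37.0% | 10.5 | 0.52 |
| 50% | 62.5% | 55.0% | 7.5 | 0.31 |

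**Step 4: unequal shares.** If lofexidine relieves symptoms before the first query, fewer may be reported on drug. Assume true TEAE rates of 75% and 60%, with 10% counted on lofexidine and 50% on placebo. Observed rates are 0.75 + 0.25 × 0.10 = 77.5% and 0.60 + 0.40 × 0.50 = 80.0%. A 15-point excess becomes a 2.5-point deficit.

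**The case against.** The strongest reply is that several safeguards already stand between a pre-dose symptom and the TEAE table.

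- Section 16.7 defines an adverse event as something new or a worsening of something pre-existing, and a study physician assesses each report. This filters at collection, and it stands. But the physician faces the same missing reference point as the analyst.
- The adverse-event listing in SAP 6.13 gives onset relative to first dosing, and 15.3.1 calls for continuous monitoring on Days 1-7, so a site can record an earlier onset. This also stands; what remains unscheduled is the severity at that time.
- SAP 6.13 tabulates withdrawal-related TEAEs separately, so many such events would be identifiable. They still count in the overall TEAE percentage and its test.
- A score of 2 or more can come from any 2 of 13 observed signs, such as yawning or dilated pupils, which subjects need not volunteer. No high prevalence for any single term follows, and the lower rows of the table in Step 3 may be far from the truth.
- Section 16.7 also relies on Appendix 6, which is not in the text available here. A pre-dose instruction there cannot be ruled out, though it would need to agree with Table 1.

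Three stronger inferences are tempting and not supported. A reader might infer that background symptoms add the same amount to every arm and thereby shrink the difference. Equal additions would leave it unchanged; at p0 = 30% the formula adds 22.5 points on lofexidine and 27 on placebo, and it is the equal share of subjects that causes the shrinkage. A reader might infer that no pre-dose grade exists, so on-drug worsening could never be shown; the Baseline SOWS-Gossop and COWS items contradict that. And a reader might take 16.7 as plainly excluding Baseline, which the structure of 14.3 does not bear out.

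**Conclusion.** The point holds as a cheap improvement. The SAP decides treatment emergence by a pre-dose severity comparison, the protocol schedules no pre-dose adverse-event query, and nothing connects the Baseline scales or examination to the rule. Some pre-existing withdrawal symptoms can therefore enter the TEAE counts.

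The direction is dilution by the factor (1 − p0) if equal shares of subjects are affected, and possibly further bias if relief before the first query differs by arm. The size cannot be determined from the documents. Under the assumed 25% versus 10% it runs from slight at p0 = 5-10% to a loss of most of the power at 50%, and those figures suppose that every case in p0 is reported and counted. The existing safeguards pull towards the lower end without closing the gap.

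**What to change.** 1. **Table 1:** put an X for the adverse-event assessment in the Baseline column.
2. **Section 15.2:** add the standard non-leading question before the first dose, recording each symptom with its severity as a pre-treatment event.
3. **Section 16.7:** reconcile with 14.3.1 so that recording explicitly starts at Baseline.
4. **SAP 6.13:** apply the treatment-emergence rule against these records, and list separately the pre-treatment events that worsened.
5. **Subjects already enrolled:** add a sensitivity table of TEAEs that excludes withdrawal-related events with Day 1 onset. It will also drop some events that truly began after dosing, so it supplements the main table.

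The cost is one question at a visit that already takes place, on a form already in use: slightly more data entry on the morning of Day 1, one extra listing and one extra table.

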**Table 1. Schedule of Study Assessments**

Activity	Randomized, Double-Blind, Placebo-Controlled (Days 1-7) followed by Open-Label, Continuation Treatment (Days 8-14)				
	Screening	Baseline	Inpatient Treatment	In/Outpatient Treatment	Study Discontinuation/End of Study*
	Days -6 to -1	Day 1	Days 1-7	Days 8-14	
C-SSRS Baseline Version		X			
C-SSRS Since Last Visit Version			X (s)	X(t)	X
Urine Drug Screen (q)	X	X	X	X	X
Telephone Follow Up (h)					X

**Abbreviations:** BP = blood pressure; C-SSRS = Columbia Suicide Severity Scale; QID = 4 times daily

\* The study discontinuation/end of study assessments/procedures should always be done upon exit from the study.

- (a) The Baseline period is the morning of admission, before randomization.
- (b) This form is to be updated at Baseline.
- (c) A chest x-ray is required only if a PPD (purified protein derivative) skin test for tuberculosis is not done, the current PPD is positive, or if a past PPD was positive.
- (d) The urine sample collected on the first day of screening will be divided into two aliquots. One sample will be sent to the central lab ( ) for urinalysis and the other sample will be used for urine drug screening and immediate “dipstick” analysis of pregnancy (females only).
- (e) During Inpatient Treatment (Days 1-7), efficacy scales will be completed daily: the Short Opiate Withdrawal Scale of Gossop 3.5 hours (±10 minutes) after the first dose of study medication followed by the other efficacy scales shortly thereafter. Efficacy scales will be completed daily before dosing during Days 8-14.
- (f) The Objective Opiate Withdrawal Scale of Handelsman (OOWS-Handelsman) will be completed at Baseline to determine final eligibility as subjects must have a score ≥2 in order to participate in the study (inclusion criterion #4).
- (g) To be done at the end of double-blind dosing and before initiating open-label dosing.
- (h) The follow-up telephone contact will be 30 days after the subject’s last dose and will include an evaluation of the subject’s current treatment status (e.g., relapse, current psychosocial treatment, successful entry into a methadone, buprenorphine, or naltrexone program) and an adverse event evaluation.
- (i) Vital signs (resting [sitting/recumbent] and standing blood pressure and pulse; respiration, and temperature) will be measured before every dose and 3.5 hours after study medication administration at 8 AM, 1 PM, and 6 PM (7 times per day).
- (j) Vital signs (resting [sitting/recumbent] and standing blood pressure, and pulse) will be measured at least once daily before dosing and 3.5 hours after dosing on Days 8-13 and once before any dose on Day 14. Oral temperature and respiration are not required measurements Days 8-14. Note that if subjects are being treated on an outpatient basis and cannot stay in the clinic for measurement of the 3.5-hour post-dose vital signs required on Days 8-13, they will be given a portable digital blood pressure machine for measurement of their vital signs at this required time point. They will also be provided a diary to record the measurements.
- (k) Baseline 12-lead electrocardiograms (ECGs) will be done on one day during the screening period, time-matched to the post randomization ECG schedule (i.e., pre-1 PM [before 1 PM dose], 4 PM [3 hours post-dose], and 5 PM [4 hours post-dose]).
  - (l) 12-lead ECGs will be done before the first daily dose, pre-1 PM dose, at 4 PM, and at 5 PM on Days 1 and 7; and before the first daily dose only on Days 2 and 4.
  - (m) 12-lead ECGs will be done before the first daily dose and 3.5 hours after first daily dose on Day 8; on Day 14, the ECGs will be done before a dose on that day.
  - (n) A finger prick blood sample will be collected concurrently with each scheduled ECG during Days 1-7.
  - (o) Clinical lab testing will be done as clinically warranted throughout the study and at the end of double-blind dosing and before initiating open-label dosing.
  - (p) A complete physical examination will be performed during screening and the physical exam form will be updated at Baseline. A complete physical examination will be performed on Day 1 (3-4 hours after randomization) and at the end of double-blind dosing and before initiating open-label dosing. During Days 8-14, a complete physical exam will be performed as clinically warranted and at discontinuation from the study.
  - (q) Urine drug screen will be done at least every other day to monitor for contraband (inpatient setting) or illicit (outpatient setting) drug use.
  - (r) A finger prick blood sample will be collected at 9 PM and 10 PM (3 and 4 hours, respectively, after the 6 PM dose).

209229

